### 1.7.1 Covid-19

For investigation subjects, all mandated hygiene measures and social distancing requirements will be followed in line with government guidelines and all relevant local guidelines will be monitored throughout the course of the clinical investigation and any changes implemented, when appropriate as the investigation progresses. Covid-19 control procedures required by the local regulations at the time of the investigation conduct to be followed by investigation subjects will be documented in the Investigator Site File (ISF).

If required per local regulation, investigation subjects and their female partners will be provided with additional information about Covid-19 and any additional requirements in relation to their participation. This information will be provided to them in written and verbal format and they will be asked to sign that they have understood this additional information before proceeding with their involvement in the clinical investigation. Investigation subjects and their female partners will be reminded that they can discontinue participation and withdraw their informed consent at any time. In case of travel restrictions for subjects and their female partners brought about by Covid-19 or additional calamitous circumstances which may prevent them from completing their on-site investigation visits, alternative methods to ensure continuity of investigation conduct and subject follow-up may be implemented. Prior to implementation, these alternative methods will be submitted to relevant authorities and Independent Ethics Committee (IEC) / Research Ethics Committee (REC) / Institutional Review Board (IRB) for approval, where needed, and the information will be provided in the Informed Consent Form (ICF) signed by the subjects and their female partners.

The risk benefit analysis for this clinical investigation has been performed to consider the potential impact of Covid-19 on the safety and wellbeing of investigation subjects and on the potential for the clinical investigation to be conducted appropriately. Risk assessments will be revisited throughout the course of the investigation and input from the Investigator will be used to identify the current local risk to the investigation, subjects and those at the site.

Oversight of monitoring and onsite/remote monitoring procedures, taking into account Covid-19 will be captured within the clinical monitoring plan for the clinical investigation.

	Clinical Investigation Plan		
	Investigation No: 5078401	Protocol Version: V2.0 08-Jun-2023	Page 24 of 62

## 1.8 Ethical Conduct of the Investigation

This clinical investigation will be conducted in accordance with this CIP and the principles set out in the Declaration of Helsinki. It will comply with International Council for Harmonisation (ICH) Good Clinical Practice (GCP), ISO 14155:2020 and applicable regulatory requirements.

## 2 INVESTIGATION OBJECTIVES AND ENDPOINTS

### 2.1 Investigation Objectives and Endpoints

The investigation endpoints based on the investigation objectives are provided in [Table 2.1](#).

**Table 2.1 Investigation Objectives and Endpoints**

Objectives	Endpoints
Primary Objective:	Primary Endpoint:
To determine the effectiveness of benzocaine, providing ancillary topical action to act as a male genital desensitiser and intended to delay male climax and prolonging the time to ejaculation, of the Test Condom A (5% benzocaine paste condom) compared with the Control NRL Condom (standard NRL condom) at prolonging time to ejaculation.	Change from baseline in Intravaginal Ejaculation Latency Time (IELT) with the Test Condom A compared to the Control NRL Condom, over a 4-week assessment period.
Secondary Objectives:	Secondary Endpoints:

 
To determine the effectiveness of benzocaine, providing ancillary topical action to act as a male genital desensitiser and intended to delay male climax and prolonging the time to ejaculation, of the Test Condom B (3% benzocaine paste condom) compared with the Control NRL Condom at prolonging time to ejaculation
 
	
 
Change from baseline in IELT with the Test Condom B compared to the Control Condom, over a 4-week assessment period.
 

 
To determine the effectiveness of benzocaine, providing ancillary topical action to act as a male genital desensitiser and intended to delay male climax and prolonging the time to ejaculation, of the Test Condom A and Test Condom B compared with the Control NRL Condom at prolonging time
 
	
 
Proportion of subjects who achieve an increase of 2 minutes from baseline in IELT in each of the Test Condom A and Test Condom B compared to the Control NRL Condom.
 
Proportion of subjects who achieve an increase of 3 minutes from baseline in IELT in each of the Test Condom A and Test
 

	Clinical Investigation Plan		
	Investigation No: 5078401	Protocol Version: V2.0 08-Jun-2023	Page 25 of 62

to ejaculation for an increase of 2, 3, and 4 minutes.	
Condom B compared to the Control NRL Condom.
 
 
Proportion of subjects who achieve an increase of 4 minutes from baseline in IELT in each of the Test Condom A and Test Condom B compared to the Control NRL Condom.
 


 
To evaluate the sexual pleasure when using the Test Condom A or Test Condom B compared with the Control NRL Condom.
 
	
 
A measure of Event-level Male Sexual (EMSEX) pleasure scale at the end of a 4-week assessment period when using Test Condom A compared with the Control NRL Condom.
 
A measure of EMSEX pleasure scale at the end of a 4-week assessment period when using Test Condom B compared with the Control NRL Condom.
 

 
To evaluate the subject's improvement at "lasting longer" for both the Test Condom A and Test Condom B compared with the Control NRL Condom.
 
	
 
A measure of Patient Global Impression of Change (PGIC) at the end of each 4-week assessment period when using the Test Condom A compared with the Control NRL Condom.
 
A measure of PGIC at the end of each 4-week assessment period when using the Test Condom B compared with the Control NRL Condom.
 

 
To evaluate the user acceptability of the Test Condom A, Test Condom B and Control NRL Condom.
 
	
User acceptability, experience and preference will be evaluated through subject perceived questions:
 
 
User acceptability, experience and preference asked at the end of a 4-week assessment period when using Test Condom A compared with the Control NRL Condom.
 
User acceptability, experience and preference asked at the end of a 4-week assessment period when using Test Condom B compared with the Control NRL Condom.
 

	Clinical Investigation Plan		
	Investigation No: 5078401	Protocol Version: V2.0 08-Jun-2023	Page 26 of 62

 
To evaluate the in-use tolerability of the Test Condom A, Test Condom B and Control NRL Condom.
 
	
 
The in-use tolerability of Test Condom A, Test Condom B and Control NRL condom, evaluated through subject perceived questions asked at the end of each 4-week assessment period.
 


 
To evaluate the performance (slippage and breakage) of the Test Condom A, Test Condom B and Control NRL condom when used during vaginal intercourse.
 
	
 
A measure of the total clinical failure rate of Test Condom A, Test Condom B and Control NRL condom.
 

 
To assess the safety of the Test Condom A, Test Condom B and Control NRL Condom.
 
	
 
Overall proportion of subjects with Adverse Events/ Adverse Device Effects (AEs/ ADEs), i.e. the occurrence of one or more AEs/ ADEs per subject.
 

## 2.2 Success Criteria

A statistically significantly greater increase in mean IELT of at least two minutes in the Test Condom A compared to the Control NRL Condom.

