	
 
• Proportion of subjects who achieve an increase of 2 minutes from baseline in IELT in each of the Test Condom A and Test Condom B compared to the Control NRL Condom.
 
• Proportion of subjects who achieve an increase of 3 minutes from baseline in IELT in each of the Test Condom A and Test Condom B compared to the Control NRL Condom.
 
• Proportion of subjects who achieve an increase of 4 minutes from baseline in IELT in each of the Test Condom A and Test Condom B compared to the Control NRL Condom.
 
• A measure of EMSEX (Event-level Male Sexual) pleasure scale at the end of a 4-week assessment period when using Test Condom A compared with the Control NRL Condom.
 
• A measure of EMSEX pleasure scale at the end of a 4-week assessment period when using Test Condom B compared with the Control NRL Condom.
 
• A measure of Patient Global Impression of Change (PGIC) at the end of a 4-week assessment period when using the Test Condom A compared with the Control NRL Condom.
 
• A measure of PGIC at the end of a 4-week assessment period when using the Test Condom B compared with the Control NRL Condom.
 
• User acceptability, experience and preference asked at the end of a 4-week assessment period when using Test Condom A compared with the Control NRL Condom.
 
• User acceptability, experience and preference asked at the end of a 4-week assessment period when using Test Condom B compared with the Control NRL Condom.
 
• The in-use tolerability of Test Condom A, Test Condom B and Control NRL condom, evaluated through subject perceived questions asked at the end of each 4-week assessment period.
 
• A measure of the total clinical failure rate of Test Condom A, Test Condom B and Control NRL condom.
 
• Overall proportion of subjects with Adverse Events/ Adverse Device Effects (AEs/ ADEs), i.e. the occurrence of one or more AEs/ ADEs per subject.
 

Success Criteria:	A statistically significant difference ( $p < 0.05$ ) in mean IELT between the Test Condom A compared to the Control NRL Condom, in favour

	Clinical Investigation Plan		
	Investigation No: 5078401	Protocol Version: V2.0 08-Jun-2023	Page 13 of 62

	of Test Condom A. A difference of two minutes is considered clinically meaningful.

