### 3.3 Determination of Sample Size

In a publication titled “A Multinational Population Survey of Intravaginal Ejaculation Latency Time (Waldinger et al., 2005)”, 500 couples were studied in a non-interventional setting over a 4-week period. The mean IELT was 8 minutes (SD = 7.1). Assuming this will be representative of the IELT of men using the standard NRL condom, and that the correlation between repeated measurements within the same subject in the 3 periods of the crossover trial will be 0.5, the table below shows the number of subjects required to detect a clinically meaningful difference of 2 minutes in mean IELT between the Test Condom A (5% Benzocaine paste) and the Control NRL Condom at 90% power, with a significance level of 5% using a two-sided paired t-test.

IELT (mins)		Number of Subjects	
Control NRL Condom	Test Condom A (5% Benzocaine paste)	Number to complete	Number randomised (10% drop out)
8	10	135	150

A sample size of 135 subjects will be sufficient to detect a difference of 2 minutes in mean IELT between the Test Condom A and the Control NRL Condom. Allowing for a dropout rate of 10%, 150 subjects will be randomised.

A 2 minute difference in IELT is considered clinically meaningful based on previous studies identified in the published literature. Shabsigh et al (2019) conducted a randomised controlled trial of topical 4% benzocaine wipes for the management of PE defined as self-reported poor control over ejaculation and an IELT of 2 minutes or less. Results showed a statistically significant increase in mean IELT of 164.80 ( $\pm 11.40$  SE) seconds after 1 month of treatment compared to placebo (110.10 s  $\pm 9.90$  SE). The clinical benefit of a difference in IELT of 1 minute or larger compared to placebo is demonstrated via a patient reported outcome known as the Index of Premature Ejaculation (IPE) whereby the men in the treatment group reported significantly higher sexual satisfaction and greater improvement in distress related to intercourse. For the purposes of relevance to the target population, a larger 2-minute difference in IELT has been selected as the relevant effect for this clinical investigation based on the subjects being healthy adult men as opposed to only men with PE (IELT <2 minutes).

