### 9.5.1 Primary Endpoint(s)

#### 9.5.1.1 Primary Analysis

The primary endpoint of the investigation is the change from baseline in IELT with the 5% Benzocaine condom versus the standard NRL condom, over a 4-week assessment period. For each subject, a mean IELT will be calculated across all intercourse episodes within a study period (baseline, assessment period 1, assessment period 2 and assessment period 3) and used for analysis. The change from baseline in IELT will be analysed using a linear mixed model using data from all three condom groups, with the primary comparison between the 5% benzocaine condom

	Clinical Investigation Plan		
	Investigation No: 5078401	Protocol Version: V2.0 08-Jun-2023	Page 53 of 62

with the standard NRL condom. The model will include fixed effects for treatment and period, a covariate for baseline IELT, and subject as a random effect. The differences between the 5% benzocaine condom with the standard NRL condom will be presented with a 95% CI and an associated p-value. Statistical significance will be assessed at the two-sided 5% level. No adjustment for multiplicity will be made since there is a single primary comparison (5% benzocaine condom versus standard NRL condom). No assumptions of normality will be checked based upon the utilization of the Generalized Linear Mixed Model (GLMM) to analyse the primary endpoint. If the model can't handle the violation, then worst case scenario a non-parametric model will be used, such as Wilcoxon signed ranks test with Hodges Lehmann estimator for treatment differences.

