### 12.2 Statistical hypotheses for primary endpoint

The differences between the 5% benzocaine condom with the standard NRL condom will be presented with a 95% CI and an associated p-value. If the GLMM can't handle the violation, then in the worst-case scenario a non-parametric test such as Wilcoxon signed ranks test will be applied.

Therefore, first we consider the null hypothesis under investigation as

$H_0$ : The beta coefficient  $\beta_1$  of the regression for the group difference from A to Control is equal to 0.

which is tested against the alternative hypothesis.

$H_1$ : The beta coefficient  $\beta_1$  of the regression for the group difference from A to Control is not equal to 0.

These hypotheses are expressed mathematically by

$$H_0: \beta_1 = 0$$

$$H_1: \beta_1 \neq 0$$

where  $\beta_1$  is the regression coefficient of IELT after 4 weeks.

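### Protocol 2.2 puts a gain of at least two minutes inside the success criterion and the synopsis does not; the 90% power applies only to the test of zero difference

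*Protocol*

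**What the plan says.** The protocol states the success criterion twice, in different terms.

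- **Protocol 2.2:** the body of the protocol sets this condition: "A statistically significantly greater increase in mean IELT of at least two minutes in the Test Condom A compared to the Control NRL Condom". The two minutes is part of it.
- **Protocol synopsis, Success Criteria row:** the rule is significance at p<0.05 for the difference "in mean IELT between the Test Condom A compared to the Control NRL Condom, in favour", with Test Condom A as the favoured product. A separate sentence adds: "A difference of two minutes is considered clinically meaningful". No minimum size is required.

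The planned test and the sample size both refer to a zero difference.

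- **Protocol 9.5.1.1:** a mixed model gives the A-minus-Control difference with a 95% CI and p-value. "Statistical significance will be assessed at the two-sided 5% level". There is no rule on the size of the estimate.
- **SAP 12.2:** under the null hypothesis the coefficient "of the regression for the group difference from A to Control is equal to 0"; the alternative is that it is not zero.
- **Protocol 3.3, repeated in SAP 12.7:** the calculation gives "the number of subjects required to detect a clinically meaningful difference of 2 minutes in mean IELT between the Test Condom A" versus control. Its operating terms are stated as "at 90% power, with a significance level of 5% using a two-sided paired t-test". The result is 135 completers and 150 randomised.

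The SAP does not restate either success criterion, and SAP 15 reports no changes from the protocol.

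**The concern.** A single result can be a success in one part of the protocol and a failure in another. A significant estimate of 1.6 minutes, for example, meets the synopsis and misses 2.2. Neither document says which text prevails.

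The sample size was built for the rule without a size condition. A trial powered to detect a true difference of 2 minutes is not powered to show an observed or proven difference of 2 minutes. Someone who takes 2.2 as the criterion and then reads 90% in 3.3 would be badly misled about the chance of success. The wording of 2.2 is also open: the two minutes could apply to the point estimate or to what the confidence interval excludes, and these are very different hurdles.

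**Working it through.** **Inputs (Protocol 3.3 and SAP 12.7):** SD of IELT 7.1 min; within-subject correlation 0.5; assumed true difference 2 min (8 versus 10); two-sided alpha 0.05; paired t-test; 135 completers; 10% dropout.

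**1. Reproduce the plan's figure.**
- SD of the paired difference = 7.1 × √(2 × (1 − 0.5)) = 7.1 min.
- Normal approximation: n = ((1.960 + 1.282) × 7.1 / 2)² = 132.4, so 133.
- Noncentral t: power is 89.9% at n = 134 and 90.1% at n = 135.
- Dropout: 135 / 0.90 = 150.

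The stated 135, 150 and 90% are all reproduced for a test against zero.

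**2. Smallest significant estimate.**
- SE = 7.1 / √135 = 0.611 min.
- t(0.975, 134) × SE = 1.978 × 0.611 = 1.21 min.

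The synopsis rule is therefore met from about 1.21 min upwards.

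**3. Chance of success at a true difference of 2 min, n = 135.**

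| Rule | Probability |
|---|---|
| Synopsis: p<0.05 in favour of A | 90.1% |
| 2.2, estimate reading: p<0.05 and estimate ≥ 2 min | 50% (simulated: 49.9%) |
| 2.2, lower-limit reading: lower 95% limit ≥ 2 min | 2.5% |

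In the second row, any estimate of 2 min or more is in practice already significant, so the probability is that of an estimate reaching its own expected value: 1 − Φ((2 − 2)/0.611) = 0.50. In the third row, the true value lies on the boundary of a two-sided 5% test, so the upper-tail probability is 0.025.

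**4. Zone of opposite verdicts.** Estimates from about 1.21 to 2.0 min pass the synopsis and fail 2.2 on the estimate reading. At a true 2 min the probability is 90.1% − 50% = about 40%.

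**5. True effect needed for 90% probability at n = 135.**
- Estimate reading: 2 + 1.2816 × 0.611 = 2.78 min.
- Lower-limit reading: 2 + (1.978 + 1.2816) × 0.611 = 3.99 min.

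**6. Sensitivity.** The 50% does not depend on SD, correlation or n, because the threshold equals the assumed effect. The 1.21 min does depend on them. With correlations of 0.3 to 0.8 (an assumed range, not in the documents) the SD of the difference is 7.1 × √1.4 = 8.40 down to 7.1 × √0.4 = 4.49. The smallest significant estimate then runs from 1.978 × 8.40/√135 = 1.43 min down to 1.978 × 4.49/√135 = 0.76 min.

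**The case against.** The strongest reply is that the inferential core is fixed and consistent. Hypothesis, alpha, model, contrast and primary population are all pre-specified, and the sample size matches the planned test. The estimate, CI and p-value will be reported whatever label is attached. The rule in 2.2 is stricter than the synopsis rule, so the type I error against zero is not inflated. The 50% is also nearly a tautology: requiring an estimate to reach the assumed true effect gives about one half at essentially any n, so it says nothing against 135 in particular.

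All of that stands, and it rules out some stronger readings that a reader might draw.

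- **That the 90% power is false.** Protocol 3.3 and SAP 12.7 attach it to a paired t-test for a difference, and for that test it is right. They never attach it to 2.2.
- **That the SAP sides with the synopsis.** SAP 12.2 gives a hypothesis, not a success rule. A test of zero is compatible with an added condition on the estimate.
- **That the result itself could be chosen after unblinding.** Only the word success is open.
- **That the wipes trial cited in 3.3 gives a probability of success here.** Its effect comes from men with PE and an IELT of 2 minutes or less, while the SD of 7.1 comes from a general survey. Protocol 3.3 itself chose a different effect because the populations differ.

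The reply does not remove the conflict. Two minutes may have been meant only as the planning effect, but 2.2 places it inside the criterion, and no other text overrides 2.2.

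**Conclusion.** The concern holds as a contradiction in the decision rule, not as an error in the sample size. The protocol carries two success criteria, the SAP chooses neither, and the stated 90% belongs only to the test of zero. At the planned true effect, the chance of meeting 2.2 is about 50% on its lenient reading and 2.5% on its strict reading. No analysis section plans a test against a two-minute margin, so the strict figure shows what the wording could imply rather than what is planned.

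The 1.21-minute lower edge and the 40% chance of opposite verdicts rest on SD 7.1, correlation 0.5, 135 completers and the paired t-test. The planned three-condom mixed model with a baseline covariate may have a different SE, which would move both. It would not move the 50%.

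This needs correcting before unblinding, because it decides whether the trial is declared a success on its primary endpoint.

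**What to change.** Put one success rule, in the same words, in the protocol synopsis, Protocol 2.2 and SAP 12.2. Nothing in the documents shows that the synopsis prevails over 2.2, so the sponsor must choose.

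- **Option (a):** two-sided p<0.05 for A minus Control from the primary mixed model, with the estimate in favour of A. Two minutes is named as the planning effect and as the benchmark for discussing the estimate and its 95% CI. This matches the planned test and the existing sample size.
- **Option (b):** keep the two-minute hurdle and say whether it applies to the estimate or to the lower 95% limit. State in Protocol 3.3 and SAP 12.7 that the probability of success at a true 2 minutes is about 50% or 2.5% respectively, and that 90% refers only to the test of zero. More subjects would not raise either figure while the true effect equals the hurdle; only a larger assumed effect would.

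The cost is wording in the protocol and SAP, with no extra subjects or data. Option (b) also means accepting the lower stated probability of success.

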## 3 INVESTIGATION DESIGN AND RATIONALE FOR DESIGN

### 3.1 Investigation Design

The investigation design is an open label, randomised, 3-way cross-over, single-centre clinical investigation evaluating the effectiveness of benzocaine in two NRL condoms in prolonging time to ejaculation compared with a standard NRL condom control in healthy male subjects who feel they ejaculate too quickly during vaginal sex.

The teat of Test Condom A and Test Condom B contains benzocaine so Test Condom A and Test Condom B are visually different from the Control NRL condom. As a result of the inherent appearance of these benzocaine condoms, subjects and their partners may notice a difference between condom types provided in each condom assessment period. The clinical investigation is therefore designed to be an open label investigation. To avoid data collection bias, each individual condom will be debranded and each set of condom types will be put in an identical box and tamper sealed. Subjects and the clinical site will not know the condom type from its primary pack and kit box. Only one condom type will be given to subjects for use in each assessment period so subjects will not be able to compare condom type side by side. The randomisation schedule will be kept only with Sponsor IMSU (Investigational Materials Supplies Unit), a CRO (Clinical Research Organisation) statistician, who is responsible for randomisation and is not involved in the analysis, and delegate site staff until database lock. Other Sponsor/CRO team members, subjects and their female partners, investigators and clinical site staff will not be provided the information of which condom type subjects have been randomised to receive.

[figure not shown]

	Clinical Investigation Plan		
	Investigation No: 5078401	Protocol Version: V2.0 08-Jun-2023	Page 27 of 62

Subjects will attend the clinical site on 5 occasions: one screening visit, three assessment period visits and one follow-up visit. Screening includes a 4-week baseline period, which allows the subject and his partner to familiarise themselves with the use of the stopwatch method and completing IELT diaries. Eligible subjects will return to the clinical site, where they will be randomised and receive the first of the three condom types (according to the randomisation schedule). Subjects will be provided with 8 condoms per condom type. The process will be repeated until all three condom types have been used. The follow-up visit will occur within 7 days after the completion of the final condom assessment period. At least a 3-day washout period, where no test condom will be used, is required before subjects attend the clinical site for visit 3 and visit 4. The 3-day washout period is to mitigate the effects on any residual benzocaine across condom types.

The investigation design is outlined in the schematic below (Figure 3-1).

